### 5.2.9 Discontinuation from trial intervention

Participants who discontinue trial treatment will remain in the trial. The remaining trial procedures should be completed as indicated by the trial protocol.

Participants may discontinue trial treatment for the following reasons:

- Participant / legal guardian request to discontinue trial intervention
- Investigator decision to discontinue a participant from the trial intervention if the participant:
  - Is pregnant
  - Experiences a serious or intolerable adverse event such that continued trial intervention would not be in the best interest of the participant
  - Develops, during the course of the trial, symptoms or conditions listed in the exclusion criteria
  - Requires a medication that is prohibited by the protocol
  - Requires early discontinuation for any other reason

The investigator may also withdraw all trial participants from the trial treatment if the trial is terminated.

The procedure for transitioning a participant off the trial drug and/or onto alternate therapy is as follows: patients will be advised to cease taking the medication immediately and return the unused medication to the researcher.

For the safety of all participants ceasing trial treatment, the protocol-specified safety evaluations should be undertaken to capture new safety events and to assess existing, unresolved safety events. All scheduled follow-ups of trial participants should also occur following treatment discontinuation, where possible.

In addition to the safety evaluations, the data to be collected at the time of trial intervention discontinuation will include the following:

- Reason for discontinuing medication
- Any adverse effects
- Involvement of other practitioners in treatment of adverse events

A dedicated Case Report Form (CRF) page will capture the date and the specific underlying reason for discontinuation of the trial intervention.

The participant should remain in the trial for scheduled visits for trial assessments (follow-up) per protocol.

## 6 RANDOMISATION AND BLINDING

An investigator not directly involved in the analysis of the trial results will prepare the randomisation schedule using block randomisation to maintain balance between treatment arms. This will be Associate [name] as she will not be directly involved in the analysis. The schedule will be provided to the pharmacist and sealed envelopes containing the treatment allocation of each randomisation code will be provided to the investigator in case of emergency.

### 6.2 Concealment mechanism

	Allocation concealment	Blinding (masking)
Definition	Unawareness of the next trial group assignment in the allocation sequence	Unawareness of the trial group to which trial participants have already been assigned
Purpose	Prevent selection bias by facilitating enrolment of comparable participants in each trial group	Prevent ascertainment, performance, and attrition biases by facilitating comparable concomitant care (aside from trial interventions) and evaluation of participants in each trial group
Timing of implementation	Before trial group assignment	Upon trial group assignment and beyond
Who is kept unaware	Trial participants, individuals enrolling them and clinicians assessing outcome measures.	One or more of the following: Trial participants, investigators, care providers, outcome assessors.
Always possible to implement?	Yes	No

### 6.3 Breaking of the trial blind

#### 6.3.1 On trial

The randomisation code for an individual participant may only be unblinded in emergency situations, where the Investigator decides a participant cannot be adequately treated without knowing the identity of their treatment allocation. Specifically, if the patient reports symptoms of vitamin C toxicity such as severe gastrointestinal upset or kidney stones, the randomisation code will be broken in order to communicate to the patient's treating physician(s) the vitamin C dosing. To break the randomisation code the Investigator must open the emergency unblinding envelopes provided, or contact the randomisation

---

facility/personnel. If any unblinding envelope is opened, the time, date, participant number and reason for opening must be documented.

Blinding is imperative in this trial to avoid bias and answer the specific research question and all researchers are aware of the importance of this.

It is not expected that inadvertent unblinding will occur due to strict randomisation and blinding protocols.

[figure not shown]
### **6.3.2 On completion of the trial**

Trial drug codes and dosing will only be available once all data collected has been entered into the trial database for every participant and the database has been finalised, except in the case of emergency as detailed above.

Patients will receive a written letter or email informing them of their treatment arm allocation as well as preliminary trial results at the end of the trial.

## 7 TRIAL VISITS AND PROCEDURES

### 7.2 Trial timeline

### 7.3 Schedule of assessments

TIME POINT**	TRIAL PERIOD							
	Enrolment	Allocation to intervention	Post-surgery					Close-out
	$-t_1$	0	Two weeks	Six weeks	Twelve weeks	Fifty weeks	Six months	Six months
ENROLMENT:	Prior to surgery							
Eligibility screen	Prior to surgery							
Informed consent	Prior to surgery							
Reference material given	Prior to surgery							
Allocation to intervention		X						
INTERVENTIONS:								
Placebo								
Vitamin C 500mg								
ASSESSMENTS:								
Two weeks post surgery			X					X
Six weeks Post surgery				X				X
Twelve weeks post surgery					X			
Twenty-six weeks post surgery							X	X

### 7.4 Description of procedures

All members of the orthopaedic team involved in assessing post-operative patients undergo an education session about the project and how to assess for CRPS. CRPS is a relatively common diagnosis that doctors of all grades should confidently be able to detect although the importance of documentation according to our diagnostic criteria will be made during the briefing. The briefing will be repeated during each rotation as the junior doctors rotate through different terms.

To determine suitability for inclusion, all elective and trauma orthopaedic theatre lists will be screened to determine patient eligibility and enrol participants. Adult patients identified as undergoing foot and ankle elective or trauma surgery, as defined as any procedure at or below the level of the distal one third of the tibia, will be deemed a potential participant. Patients will be contacted by a researcher prior to their surgery via telephone or email. If patients were admitted as an inpatient, seen in an outpatient clinic or after hours, they will be contacted by a researcher within 72 hours following their surgery. They will be

---

randomised and commenced on their treatment within 72 hours of injury or surgery. If patients are unable to commence their vitamin C/placebo treatment within 72 hours of injury or surgery they will be deemed ineligible to participate as comparative studies have commenced vitamin C supplementation the following day after surgery or injury.

If patients consented to their own surgical procedure, they will be deemed of sound mind to consent to the trial as well. Patients will be asked specifically the following questions:

- Have you taken vitamin C or any other multivitamin supplementation that contains vitamin C, in the last three months? If they answer yes, or are unsure they will be deemed ineligible to participate.
- What date and time was your surgery? If this was greater than 72 hours prior to randomisation and commencement of treatment they will be deemed ineligible.
- Are you pregnant or breastfeeding?

The following information will be collected during the initial contact with the patient should the patient consent to participation in the trial:

- Patient identifiers:
  - Age
  - Sex
  - First name/last name
  - Email address
  - Contact phone number.
- Patient demographics
  - Date of birth
  - Sex
  - Previous history of CRPS
  - Previous history of mental health condition
  - Compensable status (public patient, private health insurance, self-funded patient in private, workers' compensation, TAC, other)
- Surgical demographics
  - Date of surgery
  - Hospital where surgery was performed
  - Surgery type (elective, emergency, other)
  - Surgical site (forefoot, midfoot, hindfoot, tibia, combination, other)

The trial intervention will be administered by a researcher and commenced within 72 hours of surgery or injury. In the event that a patient sustains an injury the subsequently has surgery, their 72 hour 'clock' will commence immediately following their surgery.

At each trial visit, patients will be assessed as per the outcome criteria. Patients will be asked about their symptoms and examination documented by the clinician to specifically address the Budapest Criteria for CRPS diagnosis:

A: Does the patient report a history of:	 sensory changes (hyperaesthesia and/or allodynia)  vasomotor changes (temperature asymmetry, skin colour changes and/or skin colour asymmetry)  sudomotor/oedema changes (oedema, sweating changes or sweating asymmetry)  motor/trophic changes (decreased range of motion and/or motor dysfunction and/or weakness/tremor/dystonia and/or trophic changes of hair/nails/skin?)
B: Does the clinician observe:	 sensory changes (hyperaesthesia and/or allodynia)  vasomotor changes (temperature asymmetry, skin colour changes and/or skin colour asymmetry)  sudomotor/oedema changes (oedema, sweating changes or sweating asymmetry)  motor/trophic changes (decreased range of motion and/or motor dysfunction and/or weakness/tremor/dystonia and/or trophic changes of hair/nails/skin?)
C: Is there another diagnosis that better explains the signs and symptoms during today's history and examination?	 Yes  No
D: Is the patient's pain disproportionate to the inciting event?	 Yes  No
If the patient responds yes to three out of four questions in part A, AND the clinician observes two out of four signs in part B, AND answers yes to C and D, the patient meets the criteria for CRPS diagnosis.	 Yes  No
Does the patient meet the criteria for CRPS diagnosis?	

Patients will be examined at their review appointment by a member of the research team or treating clinician according to the following Budapest Criteria:

- A: continuing pain, which is disproportional to any inciting event
- B: The patient must report at least one symptom in three of the four following categories:
  - Sensory- reports of hyperaesthesia and/or allodynia
  - Vasomotor – reports of temperature asymmetry and/or skin colour changes and/or skin colour asymmetry
  - Sudomotor/oedema – reports of oedema and/or sweating changes and/or sweating asymmetry
  - Motor/trophic – reports of decreased range of motion and/or motor dysfunction (weakness/tremor/dystonia) and/or trophic changes (hair/nail/skin)
- C: The clinician must observe at least one sig at the time of the evaluation in two or more of the following categories:
  - Sensory- evidence of hyperalgesia (to pinprick) and/or allodynia and/or deep somatic pressure and/or joint movement
  - Vasomotor – evidence of temperature asymmetry and/or skin colour changes and/or skin colour asymmetry
  - Sudomotor/oedema – evidence of oedema and/or sweating changes and/or sweating asymmetry

- 
- Motor/trophic – evidence of decreased range of motion and/or motor dysfunction (weakness/tremor/dystonia) and/or trophic changes (hair/nail/skin)
  - D: There is no other diagnosis that better explains the signs and symptoms

If a patient is unable to attend their appointment in person, a Telehealth appointment and videoconference examination will be utilised instead of a face-to-face appointment.

This information will be recorded in RedCap database managed by Monash University. Patients who meet the above criteria will be diagnosed with complex regional pain syndrome and referred to physiotherapy for management of this condition. They will be told to continue their treatment medication. Patients will then be removed from the trial follow-up (as you cannot have CRPS twice from the same event).

Patients diagnosed with CRPS will be communicated to the lead researcher via email and subsequently entered into the trial database as meeting the outcome.

All hospital registrars and orthopaedic consultants will be given a verbal presentation to introduce the research project and the study investigators involved in the trial. This will be done at an orthopaedic weekly business meeting for approximately one hour. Education on trial design and CRPS examination and history will be provided. Study researchers will conduct follow-up history and examination.

Assessment at two weeks, six weeks, twelve weeks and twenty-six weeks is standard treatment for most bony and soft tissue injuries of the lower limb and does not deviate from normal procedure.

If a patient is diagnosed with CRPS, they will be referred to physiotherapy as per usual care. The method for which they are referred will depend on whether the patient is referred in the public or private systems:

- Public: a written referral will be made to the Physiotherapy Department at Peninsula Health. This is standard practice for a patient diagnosed with CRPS in this institution.
- Private: a written referral will be made to the patient's regular physiotherapist. If the patient does not have a regular physiotherapist, a choice of local, experienced physiotherapists will be offered for a referral and a written referral will be made. This is standard practice for management of CRPS in this system.

Patients will also be asked at each review appointment if they have adhered with the medication and if they are experiencing any side effects.

---

How has the patient felt since their last visit? (eg. fine, unwell, nauseated, in pain)

\_\_\_\_\_

---

Has the patient had any side effects to the medication such as abdominal upset, back pain, nausea or vomiting?

Yes  
 No

---

Has the patient taken the medication as prescribed?

Yes  
 No

If patients have skipped up to three consecutive dose of their medication, they will be

---

deemed 'non adherent and a note will be made on their Electronic Medical Record but will still be analysed to where they were randomised. If patients skip one dose they will be advised to simply continue the medication and not 'make up' a dose.

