#### **9.2.2 Data Capture Methods and Storage**

Study investigators will be briefed on how to record information in their assessment and consultation notes for the trial as per the protocol using RedCap. Education material and training on the use of RedCap will be provided by the Principal Investigator.

Clinicians will document the following assessment criteria in RedCap at each two week, six week, twelve week and twenty-six week follow up point:

---

A: Does the patient report a history of:

- sensory changes (hyperaesthesia and/or allodynia)
- vasomotor changes (temperature asymmetry, skin colour changes and/or skin colour asymmetry)
- sudomotor/oedema changes (oedema, sweating change or sweating asymmetry)
- motor/trophic changes (decreased range of motion and/or motor dysfunction and/or weakness/tremor/dystonia and/or trophic changes of hair/nails/skin?)

---

B: Does the clinician observe:

- sensory changes (hyperaesthesia and/or allodynia)
- vasomotor changes (temperature asymmetry, skin colour changes and/or skin colour asymmetry)
- sudomotor/oedema changes (oedema, sweating change or sweating asymmetry)
- motor/trophic changes (decreased range of motion and/or motor dysfunction and/or weakness/tremor/dystonia and/or trophic changes of hair/nails/skin?)

---

C: Is there another diagnosis that better explains the signs and symptoms during today's history and examination?

Yes  
 No

---

D: Is the patient's pain disproportionate to the inciting event?

Yes  
 No

---

If the patient responds yes to three out of four questions in part A, AND the clinician observes two out of four signs in part B, AND answers yes to C and D, the patient meets the criteria for CRPS diagnosis.

Yes  
 No

Does the patient meet the criteria for CRPS diagnosis?

---

How has the patient felt since their last visit? (eg. fine, unwell, nauseated, in pain)

\_\_\_\_\_

---

Has the patient had any side effects to the medication such as abdominal upset, back pain, nausea or vomiting?

Yes  
 No

---

Has the patient taken the medication as prescribed?

Yes  
 No

The diagnosis of CRPS will be made if the patient meets the Budapest criteria, and patients will be referred to physiotherapy for pain management. The investigator will record whether the patients was diagnosed with CRPS in the EMR and communicate this back to the patient's General Practitioner via a clinical letter (this is standard practice in the event of a post-operative complication).

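### The CRPS form's clinician-observed sensory sign repeats the symptom wording instead of the protocol's own sign definition, so the recorded sign count can differ from the definition in either direction

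*Protocol*

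**What the plan says.** The protocol sets out the Budapest criteria in sections 2.2, 3.2 and 7.4, with the same sensory wording each time. It separates the sensory symptom from the sensory sign. The symptom (criterion B) is "Sensory- reports of hyperaesthesia and/or allodynia". The sign (criterion C) is "Sensory- evidence of hyperalgesia (to pinprick) and/or allodynia and/or deep somatic pressure and/or joint movement". Criterion C is met when a sign is seen "at the time of the evaluation in two or more of the following categories".

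The assessment form in 7.4 has two matching lists. Item A begins "A: Does the patient report a history of" and item B begins "B: Does the clinician observe". Under both, the sensory line reads "sensory changes (hyperaesthesia and/or allodynia". The scoring rule counts a patient as meeting the sign requirement when "the clinician observes two out of four signs in part B".

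Section 9.2.2 reproduces the form and makes it the record: "Clinicians will document the following assessment criteria in RedCap at each two week, six week, twelve week and twenty-six week follow up point". Under section 11.3 the resulting diagnosis supplies the time-to-event outcome for the Cox regression and the six-month incidence proportion.

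**The concern.** The definition treats the sensory sign as something elicited on examination and worded differently from the complaint. The form uses the complaint's wording for both. Three of the findings named in criterion C (pinprick hyperalgesia, deep somatic pressure, joint movement) appear nowhere on the form, while hyperaesthesia, which criterion C does not name, appears as an observable sign.

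At stake is whether the recorded outcome is the one the protocol defines. Section 3.2 says the outcome method has been validated, and data collection is one of the feasibility domains under the primary objective, so the form is part of what the study is testing for a larger trial. Findings with no field on the form also cannot be recovered later from the database.

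**Working it through.** **Side-by-side reading of the sensory category**

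| Finding | Criterion C (2.2, 3.2, 7.4) | Form item B (7.4, 9.2.2) |
|---|---|---|
| Allodynia | listed | listed |
| Hyperalgesia to pinprick | listed | absent |
| Deep somatic pressure | listed | absent, unless read as allodynia |
| Joint movement | listed | absent, unless read as allodynia |
| Hyperaesthesia | not listed as a sign | listed |

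The other three sign categories (vasomotor, sudomotor/oedema, motor/trophic) agree in substance between form and definition. The threshold also agrees: two of four. Only the sensory line differs.

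**Consequence for the count**

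Let s, v, u and m be 1 or 0 for the presence of a sensory, vasomotor, sudomotor/oedema and motor/trophic sign as the definition words them. The definition's sign criterion is s + v + u + m ≥ 2.

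- There are 2⁴ = 16 patterns. Those with at least two present number 6 + 4 + 1 = 11, so 5 fail.
- *Definition positive, form negative.* Suppose the sensory sign is present only through a finding that the form omits. The form then counts v + u + m. The 11 qualifying patterns split as follows:
  - s = 1 with exactly one other category: 3 patterns. The form counts 1, so these **turn negative**.
  - s = 1 with two or three other categories: 3 + 1 = 4 patterns. The form counts at least 2, so these are unchanged.
  - s = 0 with two or three other categories: 4 patterns, unchanged.
  - Check: 3 + 4 + 4 = 11.
- *Definition negative, form positive.* Suppose the only sensory finding is hyperaesthesia. The definition has s = 0, and the form counts 1 + v + u + m. The definition fails when v + u + m ≤ 1. The form passes when v + u + m ≥ 1. They disagree when v + u + m = 1, which is 3 patterns that **turn positive** on the sign criterion.

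In both directions the disagreement arises only when exactly one other sign category is present. With item B in criterion C's wording, both sets of 3 fall to 0.

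**From pattern to patient**

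Section 3.2 counts a patient as a case if the criteria are met at any of four reviews. A true case is therefore lost only if it is missed at every visit where it would qualify. If it is missed at one visit and caught at the next, the recorded diagnosis time moves later. A pattern that turns positive on signs becomes a recorded case only if the symptom, pain and alternative-diagnosis items are also satisfied. The protocol gives no frequencies for individual signs, so no patient count or change in sensitivity can be derived.

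**The case against.** The strongest reply is that the full criteria remain in the governing text. Directly after the form, section 7.4 says patients are examined under the complete criteria, pinprick included. Section 9.2.2 repeats that diagnosis follows the Budapest criteria, and assessors are briefed at each rotation. A clinician might also tick hyperaesthesia for a heightened pinprick response, or treat pressure and joint movement as ways of eliciting allodynia. Criterion C as printed names those two as stimuli without stating the response, so that reading is open. All of this limits the effect but does not remove the contradiction: the recorded item and its scoring rule still differ from the definition, and scoring then depends on how each assessor reads the line.

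The consequence is also bounded. CRPS is a secondary outcome in a feasibility study with no formal sample size, and assessors are blinded, so mis-scoring would not be expected to differ by arm. That stands for the between-arm comparison. It gives less protection to the incidence proportion, or to the section 11.3 sensitivity analysis on individual criteria, where the sensory sign can count on its own.

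A reader might go further in three ways that the document does not support:

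- That a patient with oedema plus pain only on deep pressure or joint movement necessarily fails on the form. This needs pressure and movement to be stand-alone signs; the printed criterion does not say that pain is the response.
- That some stated fraction of true cases is missed. There is no basis for any such figure.
- That identical wording in items A and B lets one complaint be counted twice. Item B asks what the clinician observes, and the protocol's own definition uses the same terms for symptom and sign in the other three categories.

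**Conclusion.** The inconsistency is exact and appears in both places where the form is printed. Its firmest part is pinprick hyperalgesia, which criterion C names and the form leaves out. The deep-pressure and joint-movement part depends on the assessor's reading. The error can run either way: 3 of 11 qualifying sign patterns can turn negative and 3 failing patterns can turn positive, in each case only when the sensory category is decisive. These results assume that the assessor takes item B as printed and that the two-of-four rule is applied to the ticked boxes. The size in patients is unknown. No sample-size or power figure is affected.

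This is a wording mismatch in outcome recording. It does not show that the CRPS results would be biased between arms, and it is not the only fault on the form. The scoring rule also requires yes to item C, which asks whether another diagnosis explains the findings better, whereas the definition requires that there be none. Read literally, that rule fails every patient who meets the definition, whatever item B says.

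**What to change.** In item B of the form, in sections 7.4 and 9.2.2 and in RedCap, replace the sensory line with criterion C's sensory wording exactly as printed: "Sensory- evidence of hyperalgesia (to pinprick) and/or allodynia and/or deep somatic pressure and/or joint movement". Keep hyperaesthesia in item A only. Use the same wording in the assessor briefing. Copy it without additions. If the sponsor wants to settle whether pressure and joint movement are separate signs or ways of eliciting allodynia, that should be done in every statement of criterion C and on the form together.

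Correct the yes-to-C-and-D scoring rule in the same revision; changing item B alone does not make the form implement the stated criteria.

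The item B change costs one form line in RedCap, the same line in two protocol sections, and a check of the briefing material. It needs no new visit, staff or test, because the protocol's criteria already name these findings. It is best made before data collection, since findings without a field cannot be reconstructed afterwards.

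### The CRPS scoring sentence on the assessment form requires YES to another diagnosis explaining the findings, the reverse of the protocol's own definition

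*Protocol*

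**What the plan says.** Protocol sections 2.2, 3.2 and 7.4 each list the Budapest criteria, and all three end with the same exclusion: "D: There is no other diagnosis that better explains the signs and symptoms".

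The assessment form in 7.4 turns the criteria into questions and assigns the letters differently. Part A is reported symptoms and part B is observed signs. The last two items are "C: Is there another diagnosis that better explains the signs and symptoms during today's history and examination" and "D: Is the patient's pain disproportionate to the inciting event", each answered yes or no. The scoring sentence asks for three of four in part A, two of four in part B, "AND answers yes to C and D, the patient meets the criteria for CRPS diagnosis". The form then closes with its own yes/no item, "Does the patient meet the criteria for CRPS diagnosis".

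Section 9.2.2 prints the same items and the same scoring sentence as the data-capture form: "Clinicians will document the following assessment criteria in RedCap at each two week, six week, twelve week and twenty-six week follow up point". Below that form, the same section says that the diagnosis rests on meeting the Budapest criteria.

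On a positive diagnosis, 7.4 provides for physiotherapy referral, and "Patients will then be removed from the trial follow-up (as you cannot have CRPS twice from the same event".

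**The concern.** On the form, a yes to item C means that something other than CRPS is the better explanation. A scoring sentence that demands yes to C therefore admits only patients whom the protocol's definition excludes, and excludes everyone whom it admits.

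CRPS diagnosis is the protocol's only clinical efficacy outcome. Section 11.3 uses it for the Cox comparison and the six-month incidence, and section 3.2 uses it to describe who develops CRPS. These are secondary aims, but the data collection procedure is one of the primary feasibility domains in 3.1.1. A form that contradicts the outcome it records is what a feasibility study should not hand on to a definitive trial.

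**Working it through.** **1. The two rules side by side**

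| Element | Definition (2.2, 3.2, 7.4) | Form rule (7.4, 9.2.2) |
|---|---|---|
| Symptoms | at least 3 of 4 | 3 of 4 |
| Signs | at least 2 of 4 | 2 of 4 |
| Disproportionate pain | yes | yes (item D) |
| Another diagnosis explains it better | **no** | **yes** (item C) |

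The form's 3 of 4 and 2 of 4 are read as minimums, as in the definition.

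**2. Counting answer patterns**

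Four symptom boxes, four sign boxes and two yes/no items give 2^4 × 2^4 × 2 × 2 = 1024 patterns.

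- At least 3 of 4 symptoms: 4 + 1 = 5 patterns.
- At least 2 of 4 signs: 6 + 4 + 1 = 11 patterns.
- Patterns meeting the definition (C no, D yes): 5 × 11 = 55.
- Patterns meeting the form rule (C yes, D yes): 5 × 11 = 55.
- Overlap: 0, because the two rules need opposite answers to C.

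The rules disagree on 55 + 55 = 110 patterns and agree on the other 914, which are negative under both. With the form rule changed to C no and D yes, they agree on all 1024. This step needs no assumption about rates.

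**3. What mixed use would do to the comparison (illustration only)**

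The protocol gives no CRPS risk per arm, no rate of alternative diagnoses and no share of raters who would follow the sentence. Assume a true risk p in each arm, a share m in each arm who meet A, B and D but have a better alternative diagnosis, and a share q of forms scored literally, equal in both arms. Then

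observed risk = (1 − q) × p + q × m.

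Example with p = 10% (control) and 5% (vitamin C), m = 5%, q = 50%: control 0.5 × 10% + 0.5 × 5% = 7.5%; vitamin C 0.5 × 5% + 0.5 × 5% = 5.0%; ratio 5.0/7.5 = 0.667, against a true 0.50.

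| True risks (ratio 0.50) | m | q = 25% | q = 50% | q = 100% |
|---|---|---|---|---|
| 10% vs 5% | 2% | 0.531 | 0.583 | 1.00 |
| 10% vs 5% | 5% | 0.571 | 0.667 | 1.00 |
| 10% vs 5% | 10% | 0.625 | 0.750 | 1.00 |
| 30% vs 15% | 2% | 0.511 | 0.531 | 1.00 |
| 30% vs 15% | 5% | 0.526 | 0.571 | 1.00 |
| 30% vs 15% | 10% | 0.550 | 0.625 | 1.00 |

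The value at q = 100% depends on how m is set. If the alternative-diagnosis group is instead 10% of non-cases, with true risks of 15% and 7.5%, full literal use gives 0.85 × 10% = 8.5% and 0.925 × 10% = 9.25%, a ratio of 1.09. Attenuation toward 1 therefore describes mixed use; at full literal use the ratio carries no information about CRPS.

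**4. The sensory sign item**

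Section 3.2 and the criteria list in 7.4 define the sensory sign as "Sensory- evidence of hyperalgesia (to pinprick) and/or allodynia and/or deep somatic pressure and/or joint movement". Part B of the form instead repeats the symptom wording, hyperaesthesia or allodynia. The other three sign categories essentially match.

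**The case against.** A reader might infer from the scoring sentence that the trial's CRPS data will be inverted outright, with true cases recorded as negative and mimics as CRPS. The documents do not support that.

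- The correctly worded criteria follow directly after the form in 7.4, and referral and removal from follow-up are tied there to meeting those criteria. Section 9.2.2 also bases diagnosis on the Budapest criteria. The form is therefore one of two conflicting rules and not the sole decider.
- The final item is a separate clinician tick, and assessors are briefed on CRPS assessment. Some will answer by the definition.
- Only patients who also meet parts A and B and item D could be falsely scored positive, not everyone with another diagnosis.
- Items A to D are recorded at every visit, so the C/D logic can be re-derived, provided that item C was answered as the question is put.
- CRPS is a secondary outcome in a feasibility study without a formal sample size.

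All of this stands, and it makes the consequence conditional. It does not remove the contradiction. The question and the rule are complete sentences, printed twice, and nothing corrects them; section 11.3 repeats only the symptom and sign thresholds. The lettering makes a slip easier to miss. In the criteria list, C is observed signs and D is the absence of another diagnosis, so yes to both would be right there. On the form the same letters mean different things.

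A reader might also infer from part B that the form as a whole fails to capture the criteria that section 3.2 calls validated. That is too broad: the mismatch is confined to the sensory sign, and allodynia appears in both versions.

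**Conclusion.** The scoring sentence in 7.4 and 9.2.2 is wrong as written: it reverses the exclusion criterion that the protocol states three times, and no answer pattern satisfies both rules. That conclusion is purely logical.

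The consequence depends on use. Literal use would score every patient who meets the definition as negative, and would count as CRPS only patients who meet A, B and D but have a better alternative diagnosis. The likelier result is inconsistent classification between raters, which pulls the treatment comparison toward no effect. At half literal use, a true ratio of 0.50 would appear as about 0.53 to 0.75 over the assumed rates shown. These figures illustrate direction and rough size and are not estimates for this trial. They also assume that literal use is equally common in both arms, which blinding makes reasonable.

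Part of the harm is recoverable from the stored items. Visits lost after a falsely positive patient leaves follow-up are not, nor are referrals missed after a false negative. The correction should be made before the form is used. The sensory sign wording is a separate and smaller matter.

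**What to change.** In sections 7.4 and 9.2.2, replace the scoring sentence with: at least three of four in part A AND at least two of four in part B AND answers NO to C AND YES to D. This matches section 3.2 and adds no new criterion.

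State that the analysed CRPS outcome is derived from the item responses, with the clinician's final tick kept as a check.

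Separately, give the part B sensory item the sign wording of section 3.2: hyperalgesia to pinprick, allodynia, deep somatic pressure, joint movement.

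The cost is a one-line change to the form and the database, plus a minor protocol amendment. If assessments have already been made, re-derive the outcome from the stored items, and list the patients whose recorded diagnosis changes and any who left follow-up on a positive score that does not hold.
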